4.5 Premedication

To reduce the risk of adverse reactions to ATG infusion for those assigned to active treatment, methylprednisolone 0.25 mg/kg IV will be given no less than 30 minutes before each infusion of active drug. Participants assigned to the placebo group will be given a placebo (saline) infusion similar in appearance no less than 30 minutes before each infusion.

Both groups: Participants in both groups will be pre-medicated with an antihistamine and acetaminophen PO at least 30 minutes before each infusion and every 4–6 hours as needed during the infusion, as follows:

- Diphenhydramine 1.25 mg/kg/dose to a maximum of 50 mg. (*Comparable antihistamine may be used in countries who do not have diphenhydramine available*).
- Acetaminophen 10–15 mg/kg/dose to a maximum of 650 mg.

4.5.1 Cytokine Release Syndrome

With ATG infusion, the participant may experience Cytokine Release Syndrome (CRS). The signs and symptoms can span a wide clinical spectrum.

Mild Reactions: For mild (grade 1) reactions per the NCI-CTCAE for CRS, the study medication will be continued. The investigator shall take one or more of the following actions, depending on the type of the reaction:

1. Administer additional doses of antihistamine and acetaminophen.
2. Reduce the rate of infusion by 50% or more.
3. For chills and rigors, meperidine may be considered.

Moderate Reactions: For moderate (grade 2) reactions per the NCI-CTCAE for CRS, the study medication may be interrupted at the investigator's discretion. The investigator shall take the following actions, depending on the type of the reaction:

1. Interrupt infusion if any of the following occurs:
 - a. Oral temperature of $> 40.0^{\circ}\text{C}$
 - b. Symptomatic bronchospasm or pulmonary edema
 - c. Allergy-related edema
 - d. Hypotension
2. When the temperature is $< 38.5^{\circ}\text{C}$ and signs and symptoms improve, restart ATG.
3. Closely monitor the participant with pulse oximetry and a blood pressure monitoring; provide ongoing nursing evaluation until at least 2 hours after the infusion is completed.
4. If necessary, glucocorticoids can be given every 6 hours at a dose of 0.5 mg/kg of methylprednisolone or equivalent.
5. Additional supportive or resuscitative measures (such as the use of epinephrine) may be needed if clinically indicated.

Severe Reactions: For severe (grade 3) reactions or greater per the NCI-CTCAE for CRS, the study medication will be discontinued.

[figure not shown]

Figure 12. Rate Adjustments in Response to Cytokine Release Syndrome

4.5.2 Allergic Reactions

Hypersensitivity: In rare cases, people receiving ATG may experience hypersensitivity, which refers to immediate allergic, IgE mediated reactions to ATG. Such people primarily develop skin rash and respiratory distress early in the course of the infusion (usually within the first hour). For such reactions, the investigator shall take one or more of the following actions:

1. Discontinue the infusion.
2. Apply appropriate resuscitation measures, including administration of 0.3–0.5 mL aqueous epinephrine (1:1000 dilution) subcutaneously.
3. Use other resuscitative measures, as clinically indicated, including oxygen, intravenous fluids, antihistamines, corticosteroids, pressor amines, and airway management.

Mild to Moderate Reactions (Grade 1 and 2): For mild to moderate (grade 1 and 2) reactions per the NCI-CTCAE for allergic reactions, the study medication may be restarted at the discretion of the investigator.

Severe and Life-threatening Reactions: (Grade 3 and greater): For severe (grade 3) and life-threatening reactions (grade 4) per the NCI-CTCAE for allergic reactions, the study medication will be permanently discontinued.

[figure not shown]

Figure 13. Rules for Temporary interruption or discontinuation of ATG due to Hypersensitivity Reaction

4.5.3 Serum Sickness

Serum sickness from host immunization against rabbit protein may occur 7–15 days after the first dose of ATG. Study participants may require glucocorticoid treatment for supportive care. The dose will depend on the severity of signs and symptoms. Site investigators should follow the recommendations for prednisone administration (provided below) and contact the study chair for additional guidance regarding symptom management as needed for serum sickness.

For participants greater than 50kg, we recommend Prednisone as follows:

- Days 1-3: 50 mg every 12 hours
- Day 4: 40 mg every 12 hours
- Day 5: 30 mg every 12 hours
- Day 6: 20 mg every 12 hours
- Day 7: 10 mg every 12 hours

For participants less than 50kg we recommend Prednisone as follows:

- Days 1-3: 30mg every 12 hours
- Day 4: 20 mg every 12 hours
- Day 5: 10 mg every 12 hours
- Day 6: 5 mg every 12 hours
- Day 7: 5 mg once

Clinical judgment should be used in augmenting additional steroid therapy to provide the least amount of steroid required to provide symptomatic relief of serum sickness. Participants may refuse additional steroids but should be counselled that serum sickness symptoms may persist for 48-72 hours beyond the course that would be expected.

4.6 Concomitant Mediations

The use of concomitant medications will be assessed at each study visit and recorded on an appropriate source document and CRF. Participants will be asked to provide a full list of products used as each visit. This list should include any prescriptions, over the counter medications, dietary supplements or herbal preparations so investigators may review for potential interactions of any of the products in relation to the study agents.

Participants are required to receive killed (inactive) influenza vaccine for the current or upcoming season when available per local and national health guidelines. COVID-19 vaccination is strongly encouraged prior to study enrollment to meet up-to-date vaccination status per country-specific guidelines. Date of all vaccinations will be documented as applicable.

Participants will be requested not to use any of the following medications during the study.

- Any anti-diabetic medication that influences insulin sensitivity or secretion.
- Vaccination with live vaccines from 4 weeks before enrollment to 3 months following last dose of study drug is not permitted. Non-live vaccines including influenza and COVID-19 are allowed during this time period.
- Any medication that may result in immunosuppression or immunomodulation.
- Systemic glucocorticoids (unless required during ATG administration or for the treatment of cytokine release syndrome or serum sickness).

Participants will be asked to avoid consuming biotin (also called vitamin B7) or biotin containing supplements in the 2-3 days prior to study visits where lab draws are required. In an FDA Safety Communication from November 2019, it was noted that biotin can interfere with certain lab test and cause incorrect results. Participants should discuss all supplements, including multivitamins with their study staff to check if it contains biotin and the amount contained in the product and discuss alternatives and/or a plan for stopping such medication prior to study visits.

If participants receive, or if the investigator believes that participants must receive, any of the above medications, the case must be discussed with the medical monitor and/or treating physician to determine if alternatives are available. The use of these medications must be documented on the source document and CRF.

4.7 Infectious Disease Screening

All participants will be strongly encouraged to be fully vaccinated for COVID-19 with an approved COVID-19 vaccine at least 2 weeks prior to enrollment. All participants will be asked to follow guidelines for social distancing and will be asked to wear a mask when outside of their home. Participants will be assessed for COVID-19 symptoms and close exposure to an individual diagnosed with COVID-19 at each study visit and before beginning study treatment with ATG/Placebo. Participants are required to be free of COVID-19 symptoms for 14 days prior to the screening visit and before the first infusion is administered. COVID-19 testing may be performed as required per local public health or institutional guidelines. A COVID-19 test is required to be done within 7 days of the enrollment visit (infusion 1). Point of care antigen test kits are acceptable.

Beyond that, no specific infectious diseases prophylaxis is warranted in this study. This decision is based on the limited duration and dose of exposure to ATG. In lieu of active serologic or virologic monitoring strategies, all participants will be counseled on an ongoing basis on the importance of notifying their research centers about the presence of signs or symptoms suggestive of infection especially over the 3 months after the infusion. They will also be counseled on the importance of notifying the research center about potential exposures to varicella, influenza, COVID-19 or other

infectious illnesses. In addition, during the first 2 weeks post ATG infusion, all research participants will be contacted every other day and queried about the presence of signs or symptoms (e.g. fever, rhinorrhea, cough, sore throat, mouth sores, myalgia, arthralgia, etc.) that might represent markers of active infection or serum sickness. From 2 weeks post infusion to 3 months after the infusion, participants will be contacted weekly to monitor for symptoms of infection and/or illness. Specific algorithm(s) for the evaluation and management of those study participants identified as having signs and/or symptoms concerning for infection are provided in the manual of operations for this study and are directed based on the participant's specific symptomatology. This will provide general and, in some cases, specific recommendations for the assessment of study participants.

All participants will have CMV and EBV serology determined prior to study enrollment. Participants who are CMV and/or EBV seronegative must be CMV and/or EBV PCR negative within 30 days of randomization. Participants who are CMV seropositive at screening must have a negative CMV PCR and those who are EBV seropositive must have an EBV PCR <2,000 IU/mL within 30 days of randomization. All participants may not have had signs or symptoms of a CMV or EBV compatible illness lasting longer than 7 days within 30 days of randomization. Additional CMV and EBV or other infectious disease monitoring will be done only if clinically indicated.

4.8 Diabetes Management for Participants Progressing to Stage 3 T1D

Once the participant progresses to Stage 3 T1D, the participant is to receive management of their diabetes per current standards of clinical care. The goal of the treatment will be to keep the HbA1c levels within the currently recommended American Diabetes Association target range in the absence of clinically significant or severe hypoglycemia or diabetic ketoacidosis. The primary responsibility for diabetes management will be on the treating or referring diabetes care provider, but the research study team will provide additional support through regular interaction. Records of communication with the participant will provide source documentation of this interaction. Participants will not be permitted to use non-insulin pharmaceuticals for glycemic control. Insulin infusion pumps and hybrid closed loop automatic insulin delivery systems are permitted.

The Safety Monitoring Committee will evaluate individual HbA1c data outside these ranges, and will provide additional guidance to the clinical site as needed to bring glycemic control within goals. Any episode of severe hypoglycemia will be promptly reviewed by the Medical Monitor with recommendations for changes in diabetes management, if any, conveyed to the clinical site in conjunction with the Safety Monitoring Committee.

5 STUDY ASSESSMENTS

See Appendix 1 for detailed schedule of assessments

5.1 General Assessments

Study visits for all groups will occur according to the Schedule of Assessments. General assessments include:

- Medical history
- Participant experience assessments and patient reported outcome measures (i.e., quality of life, treatment satisfaction, etc.)
- Complete or directed physical exam (including Tanner Stage assessment)
- Vital Signs
- Concomitant medications
- Adverse events
- Diabetes Management (for those who progress to Stage 3)

5.2 Laboratory Assessments

The following general laboratory assessments will be performed during the study, as described in the Schedule of Assessments:

- Chemistry (sodium, potassium, chloride, CO₂, glucose, BUN, creatinine)
- Liver function tests (ALT, AST, LDH, alkaline phosphatase, total protein, albumin, total and direct bilirubin)
- Hematology (complete blood count with differential and platelets)
- Prothrombin time (PT), activated partial thromboplastin time (PTT), International Normalization Ratio (INR)
- CD4/CD8 panel
- Interferon-Gamma Release Assay Test (IGRA) *for Tuberculosis testing*
- Diabetes Autoantibodies
- Antibodies to HIV, hepatitis B (antiHBcAb, HBsAg), hepatitis C (HCV), Cytomegalovirus (CMV IgG, IgM), and Epstein-Barr Virus (EBV IgG, IgM, EBNA)
- CMV and EBV PCR
- COVID testing within 7 days of dosing (infusion 1) *Additional Covid-19 testing will be done as needed or at investigator's recommendation.*

Additional assessments include:

- Pregnancy test before ATG/Placebo infusion #1 and all study visits post-treatment for all women of reproductive age.
- COVID-19 Assessment Form

5.2.1 Pharmacokinetic and Immunogenicity Assessments

Blood samples will be obtained from a subset of participants at the timepoints indicated in the schedule of assessments (Appendix 1) to evaluate pharmacokinetic and

immunogenicity data. Pharmacokinetic assessments of the samples will include concentration-time data of ATG to obtain primary PK parameters, clearance and volume of distribution. Immunogenicity assessment will include anti-drug antibodies. Assessment of both pharmacokinetic and immunogenicity samples will be performed by a laboratory appointed by TrialNet and be analyzed using validated, specific and sensitive immunoassay methods. HLA Typing will also be performed. Samples will be collected from 12 participants in each of the following age groups: <18 years and ≥18 years at randomization.

5.3 Mechanistic Outcome Assessments

TrialNet will perform immune and genetic assays to further understand mechanisms that may be underlying the type 1 diabetes disease process and response to therapy. TrialNet proposes to evaluate the relationships between changes in immune cells and the delay in onset of T1D. Transcriptomic and serologic studies are planned. In addition, the relationship between specific genotypes and the responses to ATG may be explored. For these purposes, samples for PMBC, DNA, RNA, plasma, and serum may be obtained. The following HLA typing will also be performed: Class I (HLA-A, B, and C) and Class II (DRB, DQA, DQB).

Fecal samples will also be collected from willing participants to explore whether the gut microbiome can predict response to therapy and whether therapy induces changes in the microbiome.

5.4 Metabolic Outcome Assessments

Metabolic assessments will consist of:

- Oral Glucose Tolerance Test (OGTT)
- HbA1c
- 7-10-day blinded CGM wear following screening and all OGTT visits
- 7-10 day unblinded CGM wear following MMTT visits (for participants who progress to Stage 3 T1D)
- Mixed Meal Tolerance Test (MMTT) using BOOST® High Protein Drink (to be completed by participants who progress to Stage 3)

5.4.1 OGTT Frequency and Monitoring of Symptoms of Diabetes Progression

OGTTs will be done at month 3, 6, and then every 6 months thereafter. The study staff will contact the participants every 3 months for a monitoring call, and will obtain any history of signs or symptoms (e.g. polyuria, polydipsia, weight loss, etc) of diabetes or the finding of any random glucose > 200 mg/dl, or the diagnosis of T1D by their primary care provider. Participants will be asked to contact the study staff in-between any study visit in the event that these occur. In the event that they occur, the participant will be asked to undergo an OGTT as soon as possible and prior to the next scheduled study visit or monitoring call. As indicated in the SOA (Appendix 1), OGTTs may be performed as needed between scheduled study visits.

5.4.2 Blinded Continuous Glucose Monitoring

The participant will be instructed to wear the device continuously for 7-10 days following the screening visit and all visits with an OGTT. The participant will be masked to the blood glucose readings and will be instructed to carry on with normal daily diet and activity habits (CGM readings unmasked to participant if they progress to Stage 3 T1D during the study). Once the 7-10-day wear period has ended, participants will then mail the device back to the site for appropriate data download. See Appendix 1 for timepoints blinded CGM wear is required.

5.4.3 Unblinded Continuous Glucose Monitoring

If a participant progresses to Stage 3 T1D, the participant will continue study visits according to Appendix 2. Following all visits with an MMTT performed, the participant will be instructed to wear an unblinded CGM device continuously for 7-10 days. If a participant is wearing a CGM as part of their clinical care, the participant may opt out of using the study provided CGM device and the site will ask the participant if they would be willing to provide CGM data from the 7-10 days range per protocol.

5.5 Visit Windows

Randomization and the baseline visit must occur within 7 weeks (52 days) of having met two or more of the high-risk markers. All subsequent treatment visits and follow up visits in Appendix 1 must occur within the time limits specified below:

Visit Windows	
Visit -1:	Open window for screening for any participants with 2+ Antibodies
Visit 0:	Randomization within 7 weeks (52 days) of having met ADA Stage 2 criteria and at least one of the high-risk markers. First dose of ATG/placebo given over minimum of 6 hours and maximum of 10 hours. The infusion can be slowed or temporarily stopped to treat signs or symptoms of cytokine release with a maximum infusion time for each infusion of 10 hours.
Visit 1:	The second dose should be given no earlier than 12 hours and no later than 30 hours from the start of the first infusion. The second infusion of ATG/placebo given over a minimum of 6 hours and maximum of 10 hours. The infusion can be slowed or temporarily stopped to treat signs or symptoms of cytokine release with a maximum infusion time for each infusion of 10 hours.
Visits 1.1-1.3*	PK samples should be drawn on target days 2 and 4. Window for day 7 PK draw is ± 1 day.
Visit 2:	± 3 days

Visits 3:	± 7 days
Visits 4 to 13:	± 14 days

*subset of participants, as detailed in section 5.2.1.

5.5.1 Visit Window for Participants who Progress to Stage 3

Once a participant has reached primary endpoint (Stage 3 T1D), the participant will continue study visits according to Appendix 2. The initial study visit is to take place within 12 weeks from date of diagnosis. Study visits will then be completed every six months and within ± 14 days from the target date. The target date will be calculated from the date of the participant's initial visit post diagnosis of stage 3 T1D (1st MMTT visit). Participants who develop diabetes will be followed for a minimum of 1 year. Once follow-up within this study has finished, participants have the option to be followed in TrialNet's LIFT protocol for monitoring or other studies that are available.

5.6 Withdrawal from treatment

The study will be conducted according to the intent-to-treat principle. Once randomized into the study, a participant will be expected to undergo all scheduled follow-up assessments and will remain within the assigned treatment group for purposes of statistical analysis regardless of the actual course of treatment administered. Withdrawal from treatment does not automatically entail withdrawal from the study. While the study is actively recruiting and participant visits are conducted per Appendix 1 and 2, withdrawal from the study will only occur if the participant dies or withdraws consent. Participants who withdraw consent are classified as inactive but may again become active upon re-entry into the study, if they so choose.

Withdrawal from treatment can occur for a number of reasons, some of which are outlined below.

A participant may elect to discontinue study medications, may be unable to continue them, or may be withdrawn (temporarily or permanently) at the discretion of the Principal Investigator if s/he determines that it is unsafe to continue or there is a significant change in the risk/benefit.

Non-pregnant individuals who are withdrawn from treatment should remain in the study and undergo scheduled assessment visits as appropriate and any additional visits as needed to address ongoing AEs. OGTT tests will not occur while an individual is pregnant.

5.7 Re-Entry into the Study

In some circumstances, a participant may temporarily discontinue study participation and then later, could resume follow-up visits. If the participant decides to return for study follow-up assessments at a later date, he or she will be allowed and encouraged to do so.

5.8 Interruption of Enrollment/Trial Cessation

This section lists clinical and laboratory adverse events that will necessitate interruption of enrollment in the trial as a whole. As part of their ongoing safety review, the DSMB will make independent judgments regarding other adverse events requiring trial interruption. In addition, should the study be stopped, the FDA will be informed and the study will not resume until both the DSMB and the FDA are in agreement.

1. Any drug related death or Grade 4 SAE; During this trial, any grade 4 SAE death event will be temporarily considered unexpected and potentially drug-related until the event is reported and reviewed by the FDA and DSMB. In this event, the trial will be interrupted, including dosing of participants already enrolled and enrollment of new participants, until the grade 4 SAE or death event is reviewed by both the FDA and DSMB and both agree to the restart of trial enrollment and study agent administration.
2. Severe adverse event (defined in section 7.3) that is possibly, probably or definitely related to study treatment in any of the first 3 participants, or severe adverse events in the same organ system in any 2 participants with the exception of Grade 3 lymphopenia within the first 30 days of drug treatment. This criterion supersedes all rules below (3-8).
3. Occurrence of anaphylaxis during study treatment in any participant. Anaphylaxis is a serious allergic reaction that is rapid in onset and may cause death. Anaphylaxis is highly likely when any one of the following 3 criteria are fulfilled:
 1. Acute onset of an illness (minutes to several hours) with involvement of the skin, mucosal tissue, or both (e.g., generalized hives, pruritus or flushing, swollen lips-tongue-uvula)

AND AT LEAST ONE OF THE FOLLOWING:

 - i. Respiratory compromise (e.g., dyspnea, wheeze-bronchospasm, stridor, reduced peak expiratory flow (PEF), hypoxemia)
 - ii. Reduced Blood Pressure (BP) or associated symptoms of end-organ dysfunction (e.g., hypotonia [collapse], syncope, incontinence)
 2. Two or more of the following that occur rapidly after exposure to a likely allergen for that person (minutes to several hours):
 1. Involvement of the skin-mucosal tissue (e.g., generalized hives, itch-flush, swollen lips-tongue-uvula)
 2. Respiratory compromise (e.g., dyspnea, wheeze-bronchospasm, stridor, reduced PEF, hypoxemia)
 3. Reduced BP or associated symptoms (e.g., hypotonia [collapse], syncope, incontinence)
 4. Persistent gastrointestinal symptoms (e.g., crampy abdominal pain, vomiting)

3. Reduced BP after exposure to known allergen for that person (minutes to several hours):
 - i. Infants and children: low systolic BP (age specific) or greater than 30% decrease in systolic BP*
 - ii. Adults: systolic BP of less than 90 mm Hg or greater than 30% decrease from that person's baseline

*Low systolic blood pressure for children is defined as less than 70mmHg from 1 month to 1 year, less than (70 mmHg + [2x age]) from 1 to 10 years, and less than 90 mmHg from 11 to 17 years.

4. Any grade 3 cytokine release syndrome (according to CTCAE criteria) that does not resolve within 72 hours or grade 2 cytokine release syndrome that does not resolve within 48 hours at any time in 2 patients.
5. The occurrence of ALT or AST $\geq 3x$ ULN and bilirubin $> 2x$ ULN at any time in any one of the first 10 participants more than 2 of any ATG treated participant, with the exception of those who have been diagnosed with Gilbert's syndrome prior to randomization and have met the criteria listed in sections 4.5.1, 4.5.2 or 5.6 for this occurrence.
6. Grade 3 hypotension or any urgent care visit and/or hospitalization with or without cytokine release syndrome or anaphylaxis any time in 1 of the first 10 or more than 2 of the total ATG treated participants.
7. Grade 2 thrombocytopenia (i.e. $< 75,000/uL$) at any time in more than 2 of the ATG treated participants.
8. Clinical mononucleosis syndrome in a patient who is EBV seropositive at the time of enrollment, between 5 days and 6 months after the last dose of study drug, or at a later time if designated as probably or possibly related to study drug by the study investigator, in more than 2 patients. The syndrome may include: Grade 2 or above fever, pharyngitis, lymphadenopathy, splenomegaly, or rash, with detectable EBV viral load

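### Halting rule 2 says severe but cites the definition of serious, and its statement that it supersedes rules 3-8 can be read as cancelling them

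*Combined protocol and SAP*

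**What the plan says.** Section 5.8 opens with a mandatory statement: "This section lists clinical and laboratory adverse events that will necessitate interruption of enrollment in the trial as a whole". If the study is stopped, "the study will not resume until both the DSMB and the FDA are in agreement".

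Rule 2 has two limbs. The first is a "Severe adverse event (defined in section 7.3) that is possibly, probably or definitely related to study treatment in any of the first 3 participants". The second is severe events in the same organ system in any two participants. One exemption is given: "with the exception of Grade 3 lymphopenia within the first 30 days of drug treatment". The rule then ends: "This criterion supersedes all rules below (3-8").

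The rules below it have their own triggers. Rule 3 is "Occurrence of anaphylaxis during study treatment in any participant". Rule 4 includes "Any grade 3 cytokine release syndrome (according to CTCAE criteria) that does not resolve within 72 hours", and also grade 2 cytokine release syndrome (CRS) lasting beyond 48 hours. Rule 6 covers grade 3 hypotension, and any urgent care visit or hospitalization, in 1 of the first 10 or more than 2 of all ATG-treated participants. Rule 7 concerns grade 2 thrombocytopenia. Rule 8 concerns a mononucleosis syndrome that may include fever of grade 2 or above.

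Section 7.3 is headed Serious Adverse Event/Reaction and classifies events by outcome (death, life threat, hospitalization and so on). It does not define severe. Section 7.7 describes grade 3 events as severe, and section 8.2 equates severe with grade 3+.

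**The concern.** There are two separate faults in one mandatory safety rule.

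First, the trigger term and its cited definition disagree. The cross-reference points to seriousness, while the exemption for grade 3 lymphopenia makes sense only on a grade scale. The document does not settle which is meant. The choice bears on serum sickness, which section 6.2.1 expects in about three quarters of actively treated participants and which rule 2 does not exempt.

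Second, nothing in the protocol explains how rule 2 supersedes rules 3-8. In its ordinary sense the word means that rule 2 replaces them, which contradicts the lead-in to 5.8.

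The trial doses children from age 6, and restarting needs agreement from both the DSMB and the FDA. If the meaning is left open, it will have to be decided with events already in hand. One error would be an unintended halt for an expected toxicity. The other would be a missed halt.

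**Working it through.** **Term.** The plan gives no halting probabilities, so there is no stated figure to reproduce. The check asks whether the choice of word could change what rule 2 does, using serum sickness only.

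Inputs:
- Grade 3 rate: 6 of 6 in the Stage 2 case series (section 2.3). The exact 95% lower limit is 0.025^(1/6) = 0.541.
- Serious rate: 1 of 29. The ATG-only arm of the new-onset trial had 29 participants (section 2.3). Table 3 lists one serious serum sickness case at ages 12-17, and the 10 adults had no serious events (section 2.3.2). The exact 95% limits are 0.0009 and 0.178.
- Non-serious serum sickness in that arm: 7 events in adults (Table 2) and 13 at ages 12-17 (Table 4). Their grades are not given, so the grade 3 rate there is unknown. I take 10% to 50% as an assumed range.
- ATG arm of this trial: 68.

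Two-participant limb, assuming independent participants and no serum sickness on placebo. The average number of ATG participants to the second case is 2/p. The chance of at least two cases among 68 is 1 − (1−p)^68 − 68p(1−p)^67.

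| Reading | p | Average to second case | Chance of ≥2 in 68 |
|---|---|---|---|
| Severe, case series | 1.00 | 2/1.00 = 2.0 | certain |
| Severe, lower limit | 0.541 | 2/0.541 = 3.7 | >99.9% |
| Severe, assumed | 0.50 | 2/0.50 = 4 | >99.9% |
| Severe, assumed | 0.25 | 2/0.25 = 8 | >99.9% |
| Severe, assumed | 0.10 | 2/0.10 = 20 | 99.3% |
| Serious, 1/29 | 0.0345 | 2 × 29 = 58 | 68% |
| Serious, upper limit | 0.178 | 2/0.178 = 11 | >99.9% |

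At the lower limit of the serious rate (0.0009) the chance among 68 is 0.2%. The ranges overlap: 11 on the serious reading falls below 20 on the severe reading.

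Rule 6 also has to be counted, because it does not depend on rule 2's term. Suppose the serious case is one that is hospitalised, and the first 10 means ATG-treated participants. The chance of at least one such case in the first 10 is then 1 − (28/29)^10 = 30%. At the upper limit it is 1 − (1 − 0.178)^10 = 86%. So the averages in the table describe one limb of one rule.

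**Precedence.** This needs a reading of the text, not arithmetic. If rules 3-8 were replaced:
- One anaphylaxis below grade 4 after the third participant would meet neither rule 1 nor the first limb of rule 2. As a single case it would not meet the two-participant limb either. Rule 3 would have halted for it.
- The grade 2 events in rules 4 and 7, and grade 2 presentations under rule 8, would meet no remaining rule unless serious.

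If instead rule 2 adds to rules 3-8, all of them stay in force and the lead-in to 5.8 holds.

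**Interaction.** On the grade reading, brief grade 3 CRS in two participants would meet rule 2 even if it resolved inside the 72 hours that rule 4 allows. Rule 4's grade 3 limb would then have little effect.

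**The case against.** The strongest reply concerns precedence. Section 5.8 sets out six further rules, with a long definition of anaphylaxis, and says that the listed events interrupt enrollment. Cancelling them all in one sentence would make that text pointless, and rule 2 cannot stand in for the grade 2 rules. This stands: the additive meaning is much the likelier. A reader might infer that the sponsor has withdrawn rules 3-8, and the documents do not support that. What remains is an unexplained sentence whose literal meaning contradicts the section it sits in.

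On the term, section 7.7 ties grade 3 to hospitalization or invasive intervention. Graded strictly that way, most grade 3 cases would also be serious, and the gap would narrow. This is fair. However, the case series reports grade 3 in every child without naming a grading scale or mentioning hospitalization, and section 4.5.3 manages serum sickness with a prednisone course. Grade 3 without a 7.3 outcome is therefore possible.

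A reader might also infer from section 7.4, which provides for notifying the DSMB and FDA of grade 3 serum sickness and mentions no halt, that such cases were never meant to stop the trial. That does not follow. Section 7.4 is a reporting section. It lists anaphylaxis and CRS too, also without mentioning a halt, and rules 3 and 4 halt for both.

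Finally, other safeguards exist. The DSMB may interrupt for any event and meets about every three months on safety, serious events are reported within 24 hours, and grade 3 serum sickness is notified. These limit the harm, but none is an automatic halt.

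**Conclusion.** Rule 2 is wrong as written in its trigger term: it says severe, cites the definition of serious, and carries an exemption stated by grade. On the two-participant limb alone, the second serum sickness case would come on average after about 2 to 4 ATG participants at the case-series rate (20 if the grade 3 rate were 10%), against 58 at 1/29 (11 at the upper confidence limit).

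These figures rest on samples of 6 and 29, on an assumed grade 3 rate outside the case series, and on independence between participants. They show that the word can matter and do not predict when the trial would halt. In particular, a reader might infer that under the serious reading a halt would come late in enrollment or never. The ranges overlap, and rule 6 alone gives about a 30% chance of a halt within the first 10 ATG participants at 1/29 if the serious case is hospitalised, so that inference is not supported.

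The precedence sentence is a lesser fault. It is probably meant to be additive, but it can be read as removing the automatic halt for a single anaphylaxis and for the grade 2 events that rule 2 does not reach. No rate is claimed for those events. Neither fault touches the primary analysis or the power.

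**What to change.** Make two changes to rule 2 in section 5.8.

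(a) Replace the precedence sentence with: *Rule 2 applies in addition to rules 3-8; meeting any one rule interrupts enrollment.*

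(b) Make the term and its definition agree. The default is *Serious adverse event (section 7.3)*, because that is the definition the rule cites. If the sponsor, DSMB and FDA intended grade, write *Grade 3 or higher (section 7.7)* and add a sentence saying how expected grade 3 serum sickness, and grade 3 CRS that resolves within 72 hours, are to be counted.

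Leave the thresholds in rules 3-8 as they are. The sponsor should confirm the wording with the DSMB and FDA.

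The cost is one replaced sentence and one corrected term, by amendment, plus one sentence if the grade reading is chosen. No participants, visits or analyses are added. The downside of the default is that grade 3 serum sickness meeting no 7.3 outcome and involving no urgent care visit would be notified to the DSMB and FDA under 7.4 and would not halt enrollment automatically.
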